2.4 Analysis supporting primary objective(s) (PD analysis set)

2.4.1 Primary endpoint(s)

The primary endpoint is *Cryptosporidium* infection up to Day 10 (inclusive). This is defined as detection of oocysts

- in at least one fecal sample at \geq 72 hours after ABO809 administration
- or sooner than 72 hours if associated with symptoms suggestive of diarrheal illness, in at least one fecal sample after ABO809 administration.

Fecal stool samples will be assessed for *Cryptosporidium* infection using a commercially available diagnostic EIA test and confirmed by DFA test if the EIA is positive. Tests will be performed at a CLIA certified laboratory. Samples that test negative for *Cryptosporidium* by EIA will be reported as negative for *Cryptosporidium* without confirmation by DFA.

To overcome stool-to-stool and day-to-day oocyst shedding variability, up to 3 consecutive stool specimens, produced about 3-4 hours apart and on the same day will be tested. If at least one of the stool samples is *Cryptosporidium* positive, the participant will be considered infected. Otherwise, the participant will not be considered infected.

2.4.2 Statistical hypothesis, model, and method of analysis

The number and percentage of participants with *Cryptosporidium* infection will be tabulated by treatment. The 2-sided 80% exact confidence interval of the infection rate will also be reported.

In addition, summary tables will display the number and percentage of participants with positive EIA results (confirmed by DFA) over time (by visit) until Day 10 (inclusive) as well as until EOS. All EIA time-courses will be listed by ABO809 treatment group and cohort number and by participant.

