 To evaluate the time to onset and resolution of Cryptosporidium infection in participants who developed an infection following an oral administration of ABO809 	 Detection of fecal shedding of C. parvum oocysts by EIA CCI up to 28 days after administration of ABO809 		
	 Time to onset and time to resolution of Cryptosporidium infection following an oral administration of ABO809 		
 To assess the safety and tolerability of ABO809 	 Adverse events, vital signs, ECG findings, safety laboratory assessments including chemistry, hematology, and urinalysis results up to and including the Day 28 visit 		
	 Adverse events of special interest by telephone follow-up after Day 28 through 12 months after ABO809 administration 		

Objective(s) Endpoint(s)

Commercially Confidential Information

3 Study design

This Phase 1 Cryptosporidium CHIM study employs a single-center, open-label design to characterize the incidence of infection and associated symptoms following the administration of single doses of *C. parvum* oocysts (ABO809).

The study will enroll healthy volunteers in cohorts of approximately 10 participants who will receive ABO809 on the same day. A dose level group will receive the same ABO809 dose and can be comprised of multiple cohorts. The first dose level group will start with a cohort of 10 participants who will receive ABO809 at a dose of 1x10⁴ oocysts. The study will continue to enroll participants in the same dose level group if the desired incidences of infection and diarrheal illness are observed, up to a total of approximately 30 participants. If the desired incidences of infection and diarrheal illness are not observed, a new dose level group, receiving ABO809 at a dose of 1x106 oocysts, may be initiated. If needed to optimize the model, intermediate ABO809 doses may be evaluated (see Section 6.5).

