12.4.1 Statistical model, hypothesis, and method of analysis

The number and proportion (in percentage) of participants with *Cryptosporidium* infection will be summarized. The lower limit of the 1-sided 80% exact confidence interval of the proportions will also be reported.

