12.7 Interim analyses

12.8 Sample size calculation

12.8.1 Primary endpoint(s)

Approximately 10 participants in each cohort will be enrolled to receive ABO809. The sample size is driven by practical reasons. Assuming the true incidence of infection is 90%, there is at least 80% chance to claim that the incidence is at least 78% with a sample size of 30 participants, and 74% with a sample size of 20 participants, and 81% with a sample size of 60 participants. The calculation is based on the 1-sided 80% exact confidence interval.

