2.5.2 Statistical hypothesis, model, and method of analysis

The number and percentage of participants with clinical symptoms (diarrheal and associated symptoms) (by Day 10 (inclusive) and Day 28) and with *Cryptosporidium* infection up to Day 28 will be tabulated by treatment group. The 2-sided 80% exact confidence interval of the clinical symptom rate will be reported by treatment group.

Frequency and percentage will be presented for categorical data such as grading of stool, evidence of occult blood in stool and number of diarrhea episodes. Mean, standard deviation, median, minimum, and maximum will be presented for continuous data such as stool weight. Overlaying individual stool weight-time profiles will be generated.

Time to onset and time to resolution of infection and diarrheal illness will be summarized using Kaplan-Meier graphs with separate lines by treatment group. Median time to event for each treatment group will be estimated along with 90% confidence intervals.

Duration of infection and diarrheal illness will be summarized by treatment group.

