3.1 Primary endpoint(s)

Approximately 10 participants in each cohort will be enrolled to receive ABO809. The sample size is driven by clinical trial site capacity.

The calculation is based on the 1-sided 80% exact confidence interval.

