3.2 Secondary endpoint(s)

Commercially Confidential Information

The calculation is based

on the 1-sided 80% exact confidence interval.

4 Change to protocol specified analyses

None

5 Appendix

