5.5 Statistical models

5.5.1 Analysis supporting primary objective(s)

The primary analysis of *Cryptosporidium* infection at ≥72 hours post-administration (or sooner if associated with symptoms suggestive of diarrheal illness) up to Day 10 (inclusive is detailed in Section 2.4.1.

SAS procedure FREQ with EXACT statement for one-way tables will be used to estimate the proportion of responders (binary outcome = 1 or "Yes"), along with the associated 80% 2-sided Clopper-Pearson CI (Clopper and Pearson 1934).

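### The SAP replaces the protocol's 1-sided 80% lower limit with a 2-sided 80% interval without declaring the change, so the chances stated in protocol 12.8 do not apply to the interval that will be reported

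*SAP*

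**What the plan says.** Protocol 12.4.1, on the primary endpoint: "The lower limit of the 1-sided 80% exact confidence interval of the proportions will also be reported". The protocol summary says the same. Protocol 12.5.1 extends this limit, by treatment, to clinical symptoms by Day 10 and Day 28 and to infection up to Day 28. Protocol 12.8.1 assumes a true infection rate of 90% and states that "there is at least 80% chance to claim that the incidence is at least 78% with a sample size of 30 participants", with 74% for 20 participants and 81% for 60. Protocol 12.8.2 gives 48%, 53% and 58% for N = 20, 30 and 60, assuming a true clinical symptom rate of 70%. Both sections name the 1-sided 80% exact interval as their basis.

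The SAP names a different interval. For infection, section 2.4.2 states: "The 2-sided 80% exact confidence interval of the infection rate will also be reported". For the secondary proportions, section 2.5.2 states: "The 2-sided 80% exact confidence interval of the clinical symptom rate will be reported by treatment group". The programming text in 5.5.1 calls for the "associated 80% 2-sided Clopper-Pearson CI". Yet SAP 3.1 says: "The calculation is based on the 1-sided 80% exact confidence interval", and SAP 3.2 repeats this for the secondary endpoint. SAP Section 4, headed "Change to protocol specified analyses", has the single entry None.

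**The concern.** An 80% level means different things in the two documents. A 1-sided 80% lower limit leaves 20% in the lower tail. A 2-sided 80% interval leaves 10%, so its lower end is a 1-sided 90% limit. Two analysts, one working from each document, would report different lower limits for the primary endpoint from the same data.

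The interval is the only inferential statement planned for the primary endpoint, since the SAP has no hypothesis test and no sensitivity or supplementary analysis of it. A reader who takes the chances in protocol 12.8 and looks for them in the SAP's output will not find them, and SAP Section 4 gives no warning. The 2-sided choice appears in three SAP sections, including the programming instruction, so a slip in one sentence is unlikely.

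**Working it through.** **Inputs.** True rates 90% (infection) and 70% (clinical symptoms), N = 20, 30 and 60, and the six thresholds, all from protocol 12.8.1 and 12.8.2. The exact method is Clopper-Pearson (SAP 5.5.1). The numbers in SAP Section 3 are not visible, so the protocol's are used.

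**Formulas.** For x events in N, the exact lower limit is L(x) = the a-quantile of Beta(x, N − x + 1). Use a = 0.20 for the 1-sided 80% limit and a = 0.10 for the lower end of the 2-sided 80% interval. The chance of a claim is P(X ≥ r), with X binomial(N, true rate) and r the smallest count for which L(r) reaches the threshold.

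**Step 1: reproduce the protocol.** Take the largest r with P(X ≥ r) of at least 80%, and compute L(r) with a = 0.20.

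| Endpoint | N | r | P(X ≥ r) | L(r), 1-sided 80% | Protocol states |
|---|---|---|---|---|---|
| Infection | 20 | 17 | 86.7% | 74.14% | 74% |
| Infection | 30 | 26 | 82.5% | 78.61% | 78% |
| Infection | 60 | 52 | 85.8% | 81.57% | 81% |
| Symptoms | 20 | 12 | 88.7% | 48.09% | 48% |
| Symptoms | 30 | 19 | 84.1% | 53.99% | 53% |
| Symptoms | 60 | 39 | 83.8% | 58.80% | 58% |

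All six figures reproduce when truncated to whole percent. Exact limits at other levels (1-sided 95%, 2-sided 95%) and Wald or Wilson limits do not reproduce the set.

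**Step 2: apply the SAP interval (a = 0.10) to the same thresholds.**

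| Endpoint | N | SAP limit at the Step 1 count | Count now needed (its limit) | Chance |
|---|---|---|---|---|
| Infection | 20 | 69.58% | 18 (75.52%) | 67.7% |
| Infection | 30 | 75.10% | 27 (79.07%) | 64.7% |
| Infection | 60 | 79.25% | 53 (81.16%) | 75.2% |
| Symptoms | 20 | 43.27% | 13 (48.20%) | 77.2% |
| Symptoms | 30 | 49.99% | 20 (53.37%) | 73.0% |
| Symptoms | 60 | 55.98% | 41 (59.42%) | 66.9% |

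Every chance is below 80%, and the falls run from about 11 to 19 percentage points. For symptoms at N = 60, 40/60 gives 57.69%. If that is rounded up to 58%, the chance is 76.2%, still below 80%.

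**Step 3: thresholds the SAP interval can support.** Truncate the SAP limits in Step 2 as the protocol does: 69/75/79% for infection and 43/49/55% for symptoms. These keep the Step 1 chances of at least 82%. Truncation matters: 49.99% rounded up to 50% would require 20/30, with a chance of only 73.0%.

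**Step 4: the same data under each document.** With 27 of 30 infected, the lower limit is 82.4% under the protocol (a = 0.20) and 79.1% under the SAP (a = 0.10), a gap of 3.3 points.

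**Step 5: infection to Day 28.** Protocol 12.5.1 includes it among the proportions with a reported lower limit. SAP 2.5.2 tabulates its number and percentage but attaches the interval only to the clinical symptom rate.

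**The case against.** The strongest reply is that nothing depends on the limit. The sample size is set by practical reasons (protocol 12.8.1) and site capacity (SAP 3.1). No test or success rule uses the limit, and the dose decisions in protocol 6.5.1 use observed proportions and the totality of the data. The SAP's lower limit is the more conservative, so no claim is inflated, and the tabulated counts let anyone recover the 1-sided limit. All of this stands, and it limits the consequence.

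It can also be said that SAP 2.1 refers to analysis according to protocol Section 12, which arguably keeps the 1-sided limit and the Day 28 interval alive. That is why it is fairer to call the SAP silent on the Day 28 interval than to say it was removed. But a general reference does not override three specific sections naming another interval.

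Four stronger readings are tempting and not supported:

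- That the 12.8 figures are wrong. They are right for the interval they name.
- That the limit is the trial's only inferential output. SAP 2.5.2 and 5.5.2 give 90% intervals for Kaplan-Meier medians and for the survivor function.
- That the N = 60 figures should be deleted. Protocol Section 3 does plan a dose level for "up to a total of approximately 30 participants", but SAP 2.1 foresees pooling all cohorts for key outcomes and 12.8 does not say its figures are per dose.
- That the 70% figures concern diarrheal illness. Protocol 12.8.2 refers to clinical symptoms, which 12.5.1 defines more broadly.

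**Conclusion.** The point holds as an undeclared change to the primary analysis and a mismatch with the sample-size statement. The protocol and SAP specify different exact limits, SAP Section 3 contradicts the SAP's own analysis sections, and the entry in SAP Section 4 is incorrect. Read from the SAP interval, none of the six chances in protocol 12.8 reaches 80%: they lie between 64.7% and 77.2%, against 82.5% to 88.7% with the protocol's limit. The Day 28 infection rate has no interval named in the SAP.

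A reader might infer that the trial is under-sized or that its conclusions would change. The documents do not support that. The result rests on the protocol's assumed true rates of 90% and 70%, on independent binomial outcomes, and on the full N being analysed.

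**What to change.** Preferred: in SAP 2.4.2, 2.5.2 and 5.5.1, report the 1-sided 80% Clopper-Pearson lower limit for infection to Day 10, infection to Day 28, and the clinical symptom rates by Day 10 and Day 28. This limit is the lower bound of a 2-sided 60% interval (alpha = 0.40 in the program). Keep the 2-sided 80% interval beside it.

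Alternative: if the 2-sided interval is intended, declare it in SAP Section 4, align SAP Section 3, name an interval for infection to Day 28, and restate the protocol 12.8 thresholds for N = 20/30/60 as 69/75/79% (infection) and 43/49/55% (clinical symptoms), truncated rather than rounded.

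Optionally, label the N = 60 figures as pooled across dose groups.

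The preferred fix costs a few lines of SAP text and one program option. The alternative lowers the stated thresholds by 2 to 5 percentage points and means editing protocol 12.8. Neither changes data collection or the number of participants.

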2.4.3 Handling of intercurrent events

For participants receiving a rescue medication such as nitazoxanide during the 10 day comicling period the negative Cryptosoridium infection data collected after the start of the rescue medication will be set to missing when summarizing the time profiles as described in Section 2.4.2. The corresponding data collected during the whole study will be handled similarly. Handling of missing values not related to the intercurrent event. No missing data are expected for the primary efficacy analysis.

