2.3.4 Prior, concomitant and post therapies

Prior and concomitant medications will be coded according to the latest version of World Health Organization (WHO) Drug Reference List dictionary which employs the Anatomical Therapeutic Chemical (ATC). The number and percentage of participants taking prior and concomitant medications may be tabulated for each treatment by ATC class and PT. Concomitant rescue and other medications, procedures, and significant non-drug therapies may also be summarized by ABO809 treatment group and cohort number.

Prior medications are defined as drugs taken and stopped prior to first dose of study medication. Any medication given at least once between the day of first dose of study medication and the last day of study visit will be a concomitant medication, including those which were started before dosing and continued into the treatment period.

Rescue medication nitazoxanide

To minimize the risk of severe clinical illness, long-term asymptomatic shedding and recurrence of *Cryptosporidium* infection, nitazoxanide will be administered on Day 21 to all participants who receive ABO809 and develop a *Cryptosporidium* infection, whether or not clinical symptoms are observed.

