Nitazoxanide will be administered at 500 mg by mouth every 12 hours with food for 3 days as per the U.S. Prescribing Information, under the clinical conditions outlined below. All participants who receive ABO809 and develop an infection (i.e. oocyst shedding after Day 3 or sooner if associated with symptoms of diarrheal illness), will receive nitazoxanide on Day 21 or as soon as results of EIA analysis (and confirmed by DFA if positive) of Day 17 sample becomes available whether or not they develop clinical symptoms. There are conditions under which participants may receive nitazoxanide earlier: (i) participants with diarrhea persisting until Day 10 will start nitazoxanide on Day 10, (ii) participants with severe diarrheal illness (≥ Grade 3 as per Toxicity Grading Scale for Healthy Adult and Adolescent Volunteers Enrolled in Preventive Vaccine Clinical Trials (2007)) may receive nitazoxanide unless deemed contraindicated by the Investigator irrespective of timing. Whenever nitazoxanide treatment is administered to participants experiencing clinical symptoms, participants may be domiciled at the discretion of the Investigator until free of clinical symptoms for ≥24 hours. A second course of nitazoxanide may be considered for participants with severe diarrhea or treatment failure following first course of nitazoxanide at the discretion of the Investigator. The duration of treatment will depend upon the participant's response to therapy.

Participants will not receive nitazoxanide if:

- they did not shed oocysts at any time after Day 3 and
- they did not have diarrhea between Day 1 and Day 21 and
- there was no diagnosis of cryptosporidiosis in any of the participant's household contacts between Day 11 and Day 21

The summary of the following characteristics may be provided by ABO809 treatment group and cohort number:

- Tabulation of number of participants who required nitazoxanide on Day 21 with confirmation that all 3 doses of nitazoxanide are taken on consecutive days
- Tabulation of number of participants who required nitazoxanide earlier or if the participant requires a second course of nitazoxanide
- Tabulation of number of participants who had evidence of infection or clinical symptoms after last dose of nitazoxanide

Other rescue medications (other antiparasitic drug(s) e.g. paromomycin alone or in combination with azithromycin) will be captured under rescue medication category.

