2.5.3 Handling of intercurrent events

Stool data with grade <3 will be set to missing after the participant took the rescue medication. For "Number of days of ...", "Duration of ...", "Stool output (weight)" variables, data will be right censored if the participant took the rescue medication. Proc Lifetest and Proc Lifereg will be used to calculate the median and mean (SE), respectively. If there are convergence issues with Proc Lifereg for some visits such as those starting on Day 21 when most measurements are censored then Proc Means will be used instead.

For all Kaplan-Meier graphs, participants will be censored under the following circumstances:

- If the study ended before the subject experienced the event.
- If the subject discontinued the study before experiencing the event.
- If the subject died before experiencing the event.
- If the subject took the rescue medication before experiencing the event.

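### After rescue the SAP drops only negative EIA results and normal stools, which can inflate by-visit percentages, mainly at Days 24 and 28, depending on a denominator it does not state

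*SAP*

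**What the plan says.** SAP 2.4.2 plans a descriptive display beside the primary analysis: "summary tables will display the number and percentage of participants with positive EIA results (confirmed by DFA) over time (by visit"), to Day 10 and again to end of study. SAP 2.4.3 then sets the rule for results after rescue: "the negative Cryptosoridium infection data collected after the start of the rescue medication will be set to missing when summarizing the time profiles". It adds: "The corresponding data collected during the whole study will be handled similarly". Nothing removes positive results.

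SAP 2.5.3 has the matching rule for stool: "Stool data with grade <3 will be set to missing after the participant took the rescue medication". Grades 3 to 5 are kept. SAP 2.5.2 summarises stool grade as frequency and percentage.

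Rescue is planned for all infected participants. SAP 2.3.4 states that "nitazoxanide will be administered on Day 21 to all participants who receive ABO809 and develop a" *Cryptosporidium* infection, with or without symptoms, or once the Day 17 EIA result is known. Some start sooner: "participants with diarrhea persisting until Day 10 will start nitazoxanide on Day 10", and severe illness can be treated at any time. Those left untreated must have had no shedding after Day 3, no diarrhea and no household case.

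The SAP does not state the denominator of the by-visit percentage. SAP 2.1 says only that summaries cover all participants in the relevant population. SAP 2.4.4 and 2.4.5 plan no sensitivity or supplementary analysis for the primary objective.

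**The concern.** Missingness is made to depend on the outcome. Once a participant has been rescued, a negative EIA or a normal stool disappears and a positive EIA or a diarrheal stool remains, so any resulting bias can only be upward.

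Because rescue is triggered by having been infected at any time, this is not a rare event. The protocol expects 90-100% infection (Protocol 1.2), and SAP 2.5.3 itself foresees that most measurements are censored from Day 21. If missing results leave the denominator, the Day 24 and Day 28 percentages rest on the few participants still positive plus the few never rescued. A reader of those tables could take a cohort that has largely cleared to be one in which a large share is still shedding.

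**Working it through.** The SAP gives no figure for the effect of this rule, so there is none to reproduce. The infection rate used below is the 90% assumed in Protocol 12.8.1. That section's own statement for 30 participants reproduces: 26 or more infected has probability 0.825, and the 1-sided 80% exact lower limit at 26/30 is 78.6% (stated as 78%).

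**Inputs**
- N = 30 dosed (Protocol 12.8.1).
- m = 27 infected and rescued (90% of 30).
- u = 30 − 27 = 3 never infected, never rescued and negative. This is an assumption: an uninfected participant with diarrhea or a household case could also be rescued, which would make u smaller.
- k = rescued participants still EIA positive at the visit.
- All 30 provide a sample.

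**Formulas**
- All results kept: k/N.
- SAP rule, non-missing denominator: k/(k + u).
- SAP rule, full PD set of 30 as denominator: k/N, the same as keeping all results.

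| k | All results kept | SAP rule, non-missing denominator | SAP rule, PD-set denominator |
|---|---|---|---|
| 0 | 0/30 = 0% | 0/3 = 0% | 0% |
| 1 | 1/30 = 3.3% | 1/4 = 25% | 3.3% |
| 2 | 2/30 = 6.7% | 2/5 = 40% | 6.7% |
| 3 | 3/30 = 10% | 3/6 = 50% | 10% |

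**Expected values.** The documents do not give the probability q that a rescued participant is still positive, so q is an assumption. Two of the values tried are the protocol's figures for late shedding (Protocol 4.1): about 14% beyond Day 14 (100% − 86%, among participants with diarrhea) and 5% beyond Day 28. With k binomial (27, q) and the non-missing denominator:

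| q | All results kept | SAP rule | Chance that k = 0 |
|---|---|---|---|
| 1% | 0.9% | 6.4% | 76% |
| 5% | 4.5% | 26.5% | 25% |
| 14% | 12.6% | 52.3% | 2% |

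At 80% infected (24 rescued, 6 not) and q = 5%, the figures are 4.0% and 15.0%. In a single cohort of 10 with 9 rescued, one positive shows as 1/2 = 50% instead of 1/10 = 10%. If everyone is infected, any positive shows as 100%, and no positives leave an empty denominator.

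**Which visits.** Outpatient stool is collected in the 24 hours before each visit (Protocol Table 8-1, footnote 4), so a Day 21 sample mostly precedes a Day 21 rescue. Scheduled collection ends at Day 28. Days 24 and 28 are therefore the heavily affected visits. Earlier the effect is small: if 3 to 9 of the 27 are rescued by Day 14 and 14% of the 27 are positive, the display is 13.8% to 17.0% against 12.6%.

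**Stool grade.** Every grade kept after rescue in a rescued participant is 3, 4 or 5 by construction. Suppose 5% of the 27 rescued have a diarrheal stool (an expected count of 1.35) and 3 unrescued participants have normal stool. The share with grade 3 or higher is 1.35/30 = 4.5% with all results kept, and 1.35/4.35 = 31% under the rule.

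**The case against.** The strongest reply is that the EIA inflation depends on a denominator the SAP never states. If the general sentence in SAP 2.1 means the PD set, deleting negatives leaves every percentage unchanged. That stands, and the conclusion has to be conditional. But on that reading the rule does nothing, and results declared missing are in effect counted as negative, so the text still needs correcting.

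A reader might infer that the infection results or the estimate of clearance are distorted. The documents do not support this. Infection by Day 10 or Day 28 needs at least one positive sample (SAP 2.1.1.1), so removing negatives cannot change it, and the counts of positives are also unchanged. Time to resolution is analysed by Kaplan-Meier with censoring at rescue (SAP 2.5.3). Participant-level EIA courses are listed (SAP 2.4.2), and persistent shedding after nitazoxanide is among the events to be tabulated (SAP 2.6.1.1). What is affected is an additional descriptive display.

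It can also be argued that the rule aims at the course without rescue, since a negative after treatment may be due to the drug. That does not justify deleting only negatives. Rescue follows from ever having shed, and Protocol 4.1 expects infection to resolve by Day 21, so many of the deleted negatives would plausibly reflect natural clearance. Those never rescued are, by rule, people who never shed, so they cannot stand in for those removed. The protocol's late-shedding figures of about 14% and 5% are well below the 25% to 50% that one to three positives would show.

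**Conclusion.** The rule is wrong as written: in both SAP 2.4.3 and 2.5.3, whether a post-rescue result is kept depends on its value. With a non-missing denominator, percent EIA positive is biased upward mainly at Days 24 and 28. In the 30-participant example the display is 5 to 7.5 times the observed value for three down to one remaining positives (50/10 = 5; 25/3.3 is about 7.5), and correct at 0% if there are none. With the full PD set as denominator there is no effect on the EIA percentage. The size rests on 90% infection, on only the uninfected going unrescued, and on a post-rescue positivity that the documents do not give. It would therefore be too strong to say that the tables are strongly inflated in any event. This should be fixed, but it does not threaten the primary or the time-to-event results.

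**What to change.** In SAP 2.4.3 and 2.5.3, treat post-rescue results alike whatever their value. Keep all observed EIA results and stool grades in the by-visit tables, define the denominator as participants with a sample at that visit, and show at each visit how many have already been rescued.

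Optionally, add a second profile that drops every post-rescue result, positive or negative, and shows the number not yet rescued. It should carry a note that early rescue selects participants with persistent or severe diarrhea, so this profile may be biased downward.

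The cost is a few SAP sentences and one more row in the tables, plus one table if the optional profile is added. No new data are needed.
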